D2J. Pitfalls and solutions- Potentially larger sham dropout rates- The sham group will feel less ear pressure than the HBOT group. Since the intervention is time consuming, there may be more dropouts among those who think they are in the control group. In the majority of RCTs of behavioral interventions, there are no differences in the dropout rates of control groups^{e.g.113-117}. All subjects will be told that they will be randomized to high or low hyperbaric pressure, and that it is unknown yet if either works. At the end of the participant's 12 months participation in the trial, the participant can choose to receive HBOT treatment for which the costs will be covered by the study team. At the end of the second HBOT treatment course, an additional neuropsychological assessment will be administered to participants. The nurse might perceive the difference between HBOT and sham but will be instructed not to discuss this with participants. No non-T2D control arms- inclusion of non-T2D parallel HBOT and sham arms would show whether efficacy is specific to T2D, or generalizes to all MCI patients. However, for this pilot funding mechanism, the aim is proof of concept that HBOT improves cognition, focusing on T2D-MCI patients, who are enriched in cerebrovascular disease—the main target of HBOT—and at high risk for decline, improving statistical power. With ½ of the US elderly suffering from T2D or pre-T2D, this study has potential for broad public health impact. Collecting AD neuropathology data- *Despite associations of insulin with amyloid¹¹⁸⁻¹²⁰ and of T2D with tau pathology¹²¹, we decided against measuring them in CSF, due to a focus on vascular mechanisms, incomplete scientific evidence supporting AD neuropathology as an HBOT mechanistic target in a T2D context, and minimizing participants' burden.*

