D6. Statistical Analysis Plan- Efficacy analyses will be performed for the intent-to-treat (ITT) population, our primary analysis, and for fully and partially compliant per-protocol (PP) populations. The ITT population will include all participants in the group to which they were randomized, regardless of any protocol deviation including non-compliance, adverse events, or loss of follow-up. The PP populations will include participants in the group according to the intervention actually received, but a separate analysis will be performed for those who were fully compliant (at least 80% of sessions completed) and for those who were partially compliant (at least one session completed). A complier-average causal effect (CACE) analysis using a latent class modeling approach will also be performed on both fully and partially compliant populations. Patients missing a baseline value of a continuous efficacy outcome measure will be excluded from all analyses and maximum likelihood estimation methods will be used to handle missing data arising from an unobserved follow-up visit¹²².

Aims 1a and 1b: The primary (overall cognition) and secondary (executive functions, episodic memory domains, and computer-based tests) cognitive outcome measures (all summaries of z-scores), will each be analyzed using a mixed model analysis of covariance (ANCOVA) with time of assessment (baseline or 12 weeks) as the within-subjects factor, treatment group (HBOT vs. sham) as the between-subjects factor and baseline value of the outcome measure as the covariate. *Both, subject and 'cluster' (the variable used to identify to which group of at least 3 subjects each individual is assigned) will be modeled as random effects to account for the correlation among repeated measurements made over time within a subject as well as potential 'cluster effects' arising from blocks of at least 3 patients receiving treatment at a particular time after randomization.* An interaction term between time of assessment and treatment group will be included in each model allowing for estimation of the mean change from baseline to 12 weeks in each treatment group as well as a test for difference

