in change scores between groups. A test of parallel treatment effects across the range of baseline values will be conducted by including a three-way interaction term among time of assessment, treatment group and baseline value of the outcome variable as well as all lower order two-way interaction terms. If the three-way interaction term is statistically significant it will be retained in the final model and estimates of the difference in mean change scores between treatment groups will be evaluated at selected percentiles of the baseline distribution. Secondary mixed model ANCOVA analyses will be performed for cognitive assessments at 6 and 12 months following treatment. As an exploratory analysis, linear mixed effects models will assess the relationship between treatment group (fixed effect) and the longitudinal trend (random intercept and slope for each subject) in the primary and secondary cognitive outcome measures, assessed at 12-weeks, 6 months and 12 months following treatment. The primary hypothesis will be tested by assessing the interaction between treatment group and time of cognitive follow-up assessment, with a significant interaction indicating a difference in longitudinal cognitive trends between treatment groups. Potential confounders (age, gender, education, *duration of T2D, HbA1c, diabetes medications [insulin vs. no medications and oral agents vs. no medication], levels of atrophy and white matter hyperintensities*) will be included as covariates if there is imbalance at baseline ($p<0.1$) or association between the covariate and the response ($p<0.15$).

To explore whether specific dichotomized T2D characteristics (such as the last HbA1c level (dichotomized at 7) in the Diabetes Registry, the number of T2D complications, and the number of severe hypoglycemic episodes in the year preceding randomization) are associated with greater improvements following treatment with HBOT, mixed effects ANCOVA models similar to those for Aims 1 and 2 will add a main effect for the specific T2D characteristic and an interaction term between treatment group and the characteristic. Using the MHS dataset, we will also explore associations of dosage of the most prevalently used medications with cognitive outcomes. When potential confounders are associated with cognitive outcomes, this also may identify subgroups for which HBOT is particularly effective.

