Aim 1. Power is presented for detecting the difference in mean change (from baseline to 12 weeks) in overall cognition z-scores between the sham and HBOT treatment groups. Power calculations are based on two-sample t-tests and are conducted with a 2-sided 5% significance level (**Table 3**). A 2-sample t-test provides a more conservative power estimate than the proposed mixed model approach, which is expected to explain more variability and thus have more power to detect the same effect size with the same sample size.

The predicted mean change in the sham group from baseline to 12 weeks is -0.02 (based on the IDCD 12-week change in overall cognition). Assuming an SD of 0.50 in both the sham and HBOT groups, with a minimum sample size of 67 patients per arm, we have 80% power to detect an improvement in the HBOT group of 0.224, a “medium” effect size of 0.49. To account for an anticipated dropout rate of 13% (a reasonable estimate compared to the 5% dropout rate in our stroke study), we plan to enroll 77 patients per group for a total of 154 patients. Our HBOT trial years after mild traumatic brain injury⁷⁴ had an effect size of 0.47 for information speed processing which is clinically comparable to our primary outcome measure of overall cognition, and our HBOT trial on stroke patients⁷⁸ showed an effect size of 0.49 for the National Institutes of Health stroke scale, suggesting our detectable effect size of 0.49 is feasible.

Aim 2: As for Aim 1, power is presented for detecting the difference in the mean changes in CBF velocity and cerebral glucose utilization between the Sham and HBOT groups. Assuming a mean change in CBF velocity of -0.45 in the Sham group and an SD of 5.6 in both groups, with a minimum sample size of 67 patients per arm we have 80% power to detect an improvement in the HBOT group of 2.28, an effect size of 0.49. *To account for an anticipated dropout rate of 13%, we plan to enroll 77 patients per group for a total of 154 patients.* For cerebral glucose utilization, assuming a mean change in the sham group of -0.08 and an SD of 4.40 in both groups, with

Table 3: Two group t-test of equal means, equal n's)*			
	Outcome		
	Overall Cognition z-score	CBFV [†]	CGU [‡]
Sham Mean Change, D ₁	-0.020	-0.450	-0.08
HBOT Mean Change, D ₂	0.224	2.28	2.065
Difference in means, D ₁ -D ₂	-0.244	-2.73	-2.145
HBOT SD	0.50	5.60	4.40
Minimum N per group	67	67	67
Enrollment N per group**	77	77	77

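### As most naturally read, the 6- and 12-month cognitive effects come from baseline-plus-one-visit models, so maximum likelihood cannot use the 12-week or 6-month scores of subjects who later drop out

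*Combined protocol and SAP*

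**What the plan says.** Section D6 sets out the cognitive analysis in four steps.

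- **Missing visits.** Subjects without a baseline value are excluded. For later gaps, "maximum likelihood estimation methods will be used to handle missing data arising from an unobserved follow-up visit".
- **Primary model (Aims 1a and 1b).** A mixed model ANCOVA has time as a two-level factor (baseline, 12 weeks), treatment group, their interaction, the baseline score as covariate, and random effects for subject and cluster.
- **Later visits.** "Secondary mixed model ANCOVA analyses will be performed for cognitive assessments at 6 and 12 months following treatment". Nothing states whether these share a model with 12 weeks or with each other.
- **Joint model.** Labelled exploratory, this is a linear mixed model with a random intercept and slope per subject over 12 weeks, 6 months and 12 months. It is tested through the interaction of treatment with time.

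For imaging (Aims 2a and 2b), D6 calls the strategy similar. It spells out only the ANCOVA to 12 weeks and an exploratory joint model over 12 weeks and 12 months.

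On dropout, section D2J (Pitfalls and solutions) notes that sham subjects will feel less ear pressure and that "there may be more dropouts among those who think they are in the control group". Section D2g reports dropout of 5% to 20% in the group's earlier HBOT studies and says the team will try to assess subjects who withdraw from the intervention.

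**The concern.** The likelihood approach protects against missing-at-random dropout only through data that are in the model. If the 12-month model holds baseline and 12 months, a subject seen at 12 weeks and 6 months and then lost contributes only a baseline value, which is already conditioned on. The 12-month contrast rests on completers. It is unbiased if dropout depends on baseline and arm alone, but not if it also depends on how the subject was doing at 12 weeks.

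At stake is the plan's longer-term question. The opening summary and section C1 name the 12-month effect as an objective. D6 offers likelihood estimation as its answer to missed visits, and on this reading the visit-specific later contrasts get little of that protection. The missing information would already have been collected.

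**Working it through.** **1. The plan's own figure (12 weeks only).** Inputs from section D7: "are conducted with a 2-sided 5% significance level"; "The predicted mean change in the sham group from baseline to 12 weeks is -0.02"; "Assuming an SD of 0.50 in both the sham and HBOT groups"; "we have 80% power to detect an improvement in the HBOT group of 0.224". The difference is 0.224 + 0.020 = 0.244, and 0.244/0.50 = 0.488, the stated 0.49. The noncentral t distribution needs 67 per arm (power 0.801). With 13% dropout, 67/0.87 = 77.01, against 77 planned. The figure reproduces and this point does not touch it. D7 gives no 6- or 12-month figure.

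**2. Precision under random dropout.** Let *d* be the share lost by 12 months and *r* the correlation of 12-week and 12-month scores given baseline. The documents do not give *r*; it is assumed. With nobody lost by week 12, the variance of the 12-month contrast relative to complete data is

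- separate model: 1/(1 − d)
- joint model: (1 − r²)/(1 − d) + r²

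The ratio is 1 − r²d, so the standard error falls by 1 − √(1 − r²d). At d = 0.13, with effective n per arm 67.0 in the separate model:

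| r | SE reduction | Effective n per arm, joint |
|---|---|---|
| 0.3 | 0.6% | 67.8 |
| 0.5 | 1.6% | 69.2 |
| 0.7 | 3.2% | 71.5 |
| 0.8 | 4.3% | 73.1 |

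At d = 0.20 the reduction is 0.9% to 6.6%. Early losses shrink it. With 13% lost by week 12, 23% by 12 months and r = 0.7, the ratio is 0.51 + 0.49 × 0.77/0.87 = 0.944, an SE reduction of 2.9% instead of 5.8%.

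**3. Bias under response-related dropout.** With equal SDs, the bias of the separate model is about r × (m_HBOT − m_sham), where m is the mean 12-week residual, given baseline, among those who stay in each arm. It is zero when dropout is random.

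Simulation A (4,000 runs, 77 per arm, true 12-month effect 0.244, change SD 0.50) used equal pairwise correlations of 0.60 to 0.85 among baseline, 12 weeks and 12 months. Given baseline, that is ρ/(1 + ρ), or 0.38 to 0.46. The dropout logit started from 13% or 20% and rose by 1 per SD of poorer 12-week change where dependence applied.

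| Dependence on 12-week change | Dropout, sham/HBOT | Separate estimate | Attenuation | Joint estimate |
|---|---|---|---|---|
| None | 13/13 to 20/20% | 0.24–0.25 | none | 0.24–0.25 |
| Both arms | 17/12 to 24/17% | 0.234–0.237 | 3–4% | 0.244–0.246 |
| Sham only | 17/13 to 24/20% | 0.202–0.225 | 8–17% | 0.243–0.247 |

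Simulation B assumed stronger correlations, 0.5 to 0.7, and dropout of about 12% to 29% per arm. Attenuation was roughly 4% to 11% with dependence in both arms and about 13% to 23% with dependence in sham only; the joint model gave 0.240 to 0.246. Single scenarios of the same kind (3,000 runs):

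- r = 0.7, dropout 16%/11%, both arms: separate 0.231 (power 76%), joint 0.245 (82%). Attenuation (0.244 − 0.231)/0.244 = 5%.
- r = 0.7, dropout 28%/20%, both arms: separate 0.223 (69%), joint 0.243 (80%). Attenuation 0.021/0.244 = 9%, which by the formula needs completers' residuals to differ between arms by only 0.021/0.7 = 0.03.
- r = 0.5, dropout 18%/12%, sham only: separate 0.205 (65%), joint 0.246 (81%). Attenuation 0.039/0.244 = 16%.

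The simulations lose nobody before week 12, which favours the joint model. The ranges are not bounds: steeper dependence on 12-week change gives more bias, weaker dependence less.

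**4. What the exploratory joint model tests.** If the effect is 0.244 at 12 weeks and still 0.244 at 12 months, the between-arm difference in trend over follow-up is 0.244 − 0.244 = 0. The interaction test then targets zero although the 12-month effect is real.

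**The case against.** Several points on the other side are sound.

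- **Separate models are inferred.** A reader might take D6 to state one model per visit. It does not. The inference rests on the one-follow-up template and on the multi-visit model being described apart from it. If a joint model is intended, the text still needs to say so.
- **Earlier scores are not all lost.** A reader might conclude that no planned analysis uses them. Baseline is in every model, and the exploratory joint model uses a dropout's 12-week and 6-month scores. That model tests trend, however, and no 6- or 12-month contrast is named from it.
- **Dropout related to response is not predicted.** It is tempting to read D2J as expecting dropout to follow perceived benefit. It says only that there may be more dropout among those who think they are controls, in the context of ear pressure and a time-consuming course. It adds that most behavioral trials show no difference in control-group dropout, and it offers study-paid HBOT after 12 months, a reason to stay. D2g's follow-up of withdrawn subjects also helps. The mechanism is plausible, not expected.
- **Early dropouts gain little.** A subject lost during the 12-week course has no 12-week score to borrow.
- **The stakes are limited.** The bias in these scenarios is toward the null, the contrasts are secondary, and the trial calls itself a pilot.

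These points limit the size and certainty of the concern. They do not supply a planned 6- or 12-month estimate that uses the intermediate scores.

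**Conclusion.** The point holds for the secondary 6- and 12-month cognitive contrasts, on the natural but unstated reading that each model has one follow-up visit. Those contrasts are then in effect completers' analyses, and the promised likelihood handling does not extend to dropout that depends on 12-week or 6-month performance. The main issue is conditional bias; the precision loss at the planned dropout is small. The sizes in the working rest on assumed correlations, dropout rates and selection strengths.

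The documents do not support extending this to the primary result. No post-baseline visit precedes 12 weeks, so the primary contrast barely changes and the 67 and 77 per arm stand. For imaging, the point applies only if a separate 12-month ANCOVA is meant, which can be read in only through the reference to a similar strategy.

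**What to change.** State in D6 that the secondary 6- and 12-month treatment effects come from one likelihood-based repeated-measures model of the 12-week, 6-month and 12-month scores. It would have categorical visit, visit-by-treatment and baseline-by-visit terms, an unstructured within-subject covariance and the cluster random effect. The treatment contrast at each visit is read from it. Do the same for any 12-month imaging contrast, using 12 weeks and 12 months. The primary 12-week contrast may be read from the same model or kept as planned, and the exploratory trend model can stay.

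The cost is SAP wording and a few more covariance parameters to fit. It needs no new subjects, visits or data. The result is valid under missing at random given the observed scores; it does not protect against dropout that depends on unobserved scores.

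### The SAP attaches the primary hypothesis to a treatment-by-follow-up-time interaction in a model it has just called exploratory, at odds with the baseline-to-12-week change contrast that the plan puts first and powers

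*Combined protocol and SAP*

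**What the plan says.** D6, Aims 1a and 1b, sets out three layers for the cognitive outcomes.

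- **12-week model.** A mixed-model ANCOVA with "time of assessment (baseline or 12 weeks) as the within-subjects factor" and the baseline value as covariate. Its time-by-treatment term is described as "allowing for estimation of the mean change from baseline to 12 weeks in each treatment group as well as a test for difference"; what is compared between the arms is the change score.
- **Later visits.** "Secondary mixed model ANCOVA analyses will be performed for cognitive assessments at 6 and 12 months following treatment".
- **Slope model.** "As an exploratory analysis, linear mixed effects models will assess the relationship between treatment group (fixed effect) and the longitudinal trend", with a random intercept and slope per subject, in the "primary and secondary cognitive outcome measures, assessed at 12-weeks, 6 months and 12 months following treatment".

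The sentence after the slope model reads "The primary hypothesis will be tested by assessing the interaction between treatment group and time of cognitive follow-up assessment". It goes on to interpret a significant result as a difference in longitudinal trends between the arms.

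D7, Aim 1, and Table 3 power only the between-arm difference in mean change from baseline to 12 weeks. For imaging (D6, Aims 2a and 2b) the same slope model is exploratory, and no sentence about a primary hypothesis follows it.

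**The concern.** The two tests answer different questions. The 12-week contrast asks whether HBOT changed cognition more than sham by the end of treatment. The interaction asks whether the arms move apart or together over visits that all fall at or after the end of treatment. The Aims state the hypothesis as improvement compared with sham, and that is the first question.

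An analyst who follows the sentence literally would let the second question decide the trial. With only the listed visits in the model, a lasting benefit sits in the intercept difference and is invisible to the named test. A fading benefit could produce a significant interaction that reflects waning. An analyst who instead infers the intent has to override the only sentence that names a test for the primary hypothesis. That choice should not be left open until the data are in.

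**Working it through.** **1. Does other text settle which test is primary?**

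- The Aims and C1 list short-term and 12-month effects without ranking them.
- D2h defines the primary composite without a time point or contrast.
- "Efficacy analyses will be performed for the intent-to-treat (ITT) population, our primary analysis" concerns the analysis population.
- D6 order, the secondary label on the later ANCOVAs, the exploratory label on the slope model and D7 all point to the 12-week contrast, but none calls it primary.

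So one explicit sentence stands against an implied hierarchy.

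**2. Reproduce the plan's figure (D7, Aim 1; Table 3).**

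- Difference: 0.224 − (−0.020) = 0.244. SD of change 0.50. Effect size 0.244/0.50 = 0.488 (plan: 0.49).
- Two-sample t-test, two-sided 5%, 67 per arm: noncentrality 0.488 × √(67/2) = 2.82 on 132 df, power **80.1%**. With 66 per arm it is 79.5%, so 67 is reproduced.
- Enrolment: 77 × 0.87 = 66.99, consistent with 77 per arm.

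**3. What the interaction estimates.** Let D(t) be the HBOT-minus-sham difference at follow-up time t. With complete visits the interaction is the slope difference

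b = Σ(t − t̄)D(t) / Σ(t − t̄)².

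If D(t) = 0.244 at 12 weeks, 6 and 12 months, the numerator is 0.244 × Σ(t − t̄) = 0. The interaction is zero and the test rejects at 5.0%, whatever the sample size.

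**4. Other durability patterns (illustrative).** The documents give no residual SD, slope SD or durability profile. Assumptions: residual SD 0.50/√2 = 0.354; slope SD 0 to 0.3 per year; linear change; 67 per arm kept to 12 months; no cluster effect. The SD of a per-subject slope is √(0.354²/Sxx + slope SD²), where Sxx = Σ(t − t̄)². Each range runs from slope SD 0 to 0.3.

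| Pattern | Visits at 0, 0.5, 1 year after treatment (Sxx 0.50) | Visits at 12/52, 0.5, 1 year from baseline (Sxx 0.305) |
|---|---|---|
| Maintained | 5.0% | 5.0% |
| Half lost by 12 months | 28.9% to 22.5% | 29.6% to 25.2% |
| All lost by 12 months | 80.1% to 67.2% | 81.2% to 73.1% |
| Maintained, baseline added as a fourth visit | 62.9% to 43.0% | 63.5% to 49.5% |

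**5. Would the D6 12-week model hold its 5% level?** D6 uses baseline both as a response row and as a covariate. Take unit variances and correlation ρ between baseline and 12 weeks, with no cluster effect.

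- The common baseline coefficient is (1 + ρ)/2.
- The residuals of a subject's two rows then have covariance −(1 − ρ)²/4. This is negative, so a non-negative subject variance is estimated at zero.
- The pooled residual variance is (1 − ρ)(3 + ρ)/4. The model therefore gives the contrast a variance of 4 × (1 − ρ)(3 + ρ)/(4n), against a true 4(1 − ρ)/n. The ratio is (3 + ρ)/4.
- Null rejection is about 2Φ(−1.96√ratio). For assumed ρ of 0.5, 0.7 and 0.9 the ratio is 0.875, 0.925 and 0.975, giving 6.7%, 5.9% and 5.3%. Simulation with 67 per arm gave about 6.6%, 6.2% and 5.6%.

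Naming that term as primary without changing the model would therefore not guarantee the stated 5%.

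**The case against.** The strongest reply is that the structure already settles the matter. The sentence follows directly on an exploratory label, and its ending interprets that model, so it may only mean the main hypothesis of the exploratory analysis. The 12-week model comes first and is the only one powered. This makes loose or misplaced wording a likely explanation, and it limits how serious the point is. It does not remove the point: the sentence says primary hypothesis without qualification, and nothing else in the plan assigns that hypothesis to a test.

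Three stronger readings are tempting and not supported.

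- **A treatment that works will give a negative primary result.** This needs the sentence to be followed literally, baseline to be absent from the slope model and the benefit to be fully maintained. The first is doubtful. The second is a reading of the visit list, since D6 does not say how baseline enters. The documents give no durability profile for the third.
- **The type I error is up to 10%.** That is the general bound for two 5% tests when either may be claimed. The plan nowhere grants that choice.
- **The trial is mis-sized.** The sample size reproduces; the defect is only in which test is named.

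It is also fair to say that naming the 12-week term does not close every data-dependent step. D6 retains a three-way time, treatment and baseline interaction when it is significant, and there is then no single treatment effect to test. The fix has to deal with that. The covariate rules based on p-values in D6 are a separate matter.

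**Conclusion.** The point holds as an internal conflict over which test is primary. The only sentence that names a test for the primary hypothesis points to an interaction in an exploratory model, while the rest of D6 and D7 imply the baseline-to-12-week difference in change.

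Two figures carry the conclusion. The 12-week contrast has 80.1% power on the plan's own inputs. The interaction has a 5.0% rejection rate for a maintained benefit, exact by construction but conditional on baseline not being a visit. If baseline were a visit, power for a maintained benefit would be 43% to 64% under the assumptions in the working, still below the planned 80%. These figures and those for a fading benefit are illustrations and should not decide how serious the point is. The wording is probably an oversight, but it governs the trial's central test and is cheap to correct.

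**What to change.** Replace the sentence in D6 with text such as:

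> The primary hypothesis is tested once, by the HBOT-minus-sham difference in change in overall cognition from baseline to 12 weeks (ITT, two-sided 5%), from the model without the three-way baseline interaction; results by baseline percentile are supportive. The treatment-by-time interaction over 12 weeks, 6 and 12 months is exploratory and describes whether the arms diverge or converge after treatment.

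In the 12-week model, enter baseline once, either as a response row or as a covariate but not both, so that the standard error supports the 5% level. State how baseline enters the slope model: as a visit, as a covariate or not at all. Keep the secondary 6- and 12-month ANCOVAs for durability.

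The cost is a few sentences of SAP wording. The contrast is the one D7 already powers, so sample size, visits and data collection stay as they are.

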T2FLAIR images will be segmented according to methods previously used by our group¹⁰⁶. WMH will be used as covariates in the second-level analysis.

FDG-PET: [name] [name], Chair of the Nuclear Medicine Department at Sheba, will oversee acquisition of [F18]FDG on a Philips Gemini GXL + PET scanner in 3D mode.

[F18]FDG-PET Acquisition: Participants will be studied after a minimum 4 hour fast (water allowed). Because participants with glucoregulatory dysfunction are being imaged, blood glucose will be closely monitored prior to the injection of [F18]FDG. Blood glucose prior to [F18]FDG administration must be ≤ 180 mg/dL for [F18]FDG to be injected. Following injection with 5.0 ± 0.5 mCi of [18F][F18]FDG participants will remain awake but relaxed in a quiet room. Imaging will begin 45 min. post injection, and the scan acquired as six 5-min. frames. A 5-min. transmission scan will be acquired following the emission scan. The dynamic PET data will be reconstructed using ECAT v7.2.2 software. A filtered back projection algorithm (DIFT) will be used with brain mode sinogram trimming, zoom = 2.8, and a 4mm Gaussian filter to a reconstructed image of 128 x 128 x 63 voxel matrix (voxel size = 1.84mm x 1.84mm x 2.43mm). The PET data will be corrected for the attenuation of annihilation radiation (using segmented attenuation maps), scanner normalization, and scatter radiation.

[F18]FDG image processing: Data will be transferred to the ADRC imaging lab at the UW-Madison using a secure protocol our group has in place. The reconstructed images will be used for comparison of regional differences of [F18]FDG uptake in the targeted areas of the brain. The dynamic [F18]FDG will first be corrected for frame to frame motion using SPM12 software. Any frames with excessive motion will be discarded from further processing. The data will then be summed to create a single image representing [F18]FDG uptake in the brain from the period of 45–75 minutes.

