Aims 2a and 2b: CBF and cerebral glucose utilization will be analyzed with a similar strategy to Aims 1a and 1b except that there will be no 6 month assessment. Mixed effects ANCOVA models will be used to compare changes in these outcome measures from baseline to 12 weeks following treatment, and, as exploratory analyses, linear mixed effects models will be used to assess relationships between treatment group (fixed effect) and the longitudinal trend (random intercept and slope for each subject) in MRI-ASL and FDG-PET outcome measures, assessed at 12-weeks and 12 months following treatment. Vascular effects of HBOT vs. Sham: Since CBF derived from ASL perfusion may represent combined effects of neural metabolism and vascular effects, a secondary mixed effects ANCOVA model (similar to Aim 2b) of vascular changes from baseline to 12 weeks as measured by ASL CBF will adjust for neural metabolism derived from FDG-PET.

Aim 3: Outcome measures (changes in CBF and cerebral glucose utilization) identified as having significant associations with treatment group in Aims 2a and 2b will be further explored as mediators of the relationship between treatment group and the change in cognition. To ensure that measurement of mediator

variables precedes measurement of cognition, we will define the outcome as the change in cognition from baseline to 12 months, and the mediators as changes in CBF and cerebral glucose utilization, from baseline to 12 weeks. The product of coefficients approach will be used within a multiple mediator modeling framework to provide point estimates of both the specific indirect effect (i.e. the effect of treatment group on the change in cognition from baseline to 12 months via a mediator among other mediators in the model) and the total indirect effect (i.e. the sum of specific indirect effects for all mediators in the model). The bootstrapping method⁹³ will be used in each multiple mediator model to compute bias-corrected standard errors (and 95% confidence intervals) for the specific and total indirect effect point estimates.

D7. Power Analysis and sample size justification

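### Covariates beyond the baseline score are selected by p-value tests on the trial's own data, so the adjusted model, possibly including the primary one, is not fixed in advance

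*Combined protocol and SAP*

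**What the plan says.** All references are to the Combined protocol and SAP.

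- **D6, Aims 1a and 1b, main model.** The overall, executive, memory and computer-based composites "will each be analyzed using a mixed model analysis of covariance (ANCOVA"). The model has time, treatment, their interaction, and random effects for subject and cluster, with the "baseline value of the outcome measure as the covariate". That baseline score is unconditional.
- **D6, Aims 1a and 1b, further covariates.** After the exploratory longitudinal model comes a list that opens "Potential confounders (age, gender, education" and goes on to diabetes duration, HbA1c, two diabetes-medication contrasts, atrophy and white matter hyperintensities (WMH). This is eight variables, or nine model terms. They "will be included as covariates if there is imbalance at baseline", and the entry condition in full is "imbalance at baseline ($p<0.1$) or association between the covariate and the response ($p<0.15").
- **D6, Aims 2a and 2b.** The approach carries over to imaging: "CBF and cerebral glucose utilization will be analyzed with a similar strategy to Aims 1a and 1b".
- **D2j, MRI image processing.** Here WMH appears with no condition: "WMH will be used as covariates in the second-level analysis".

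No additional covariate set is fixed. No model is named as primary with the selected model as a sensitivity analysis.

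**The concern.** Neither test is a sound reason to adjust. Allocation is 1:1 at random (D2d), so a small p-value for a baseline difference reflects chance and says nothing about whether the variable predicts cognition. The second test uses the outcome to build the model that then tests treatment on the same outcome.

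The rule is also incompletely written. It does not say whether the response is the 12-week score or the change, or whether treatment is in the screening model. Two analysts could follow the text and reach different models. Because each outcome is modelled separately, the selected sets can differ between overall cognition, its two domains and the imaging measures.

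At stake is whether a reader can know, before the data are seen, which adjusted estimate counts as the primary result.

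**Working it through.** **1. The plan's own figure.** D7 gives a difference of 0.224 − (−0.020) = 0.244, SD 0.50, two-sided 5% and 80% power.

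- Normal approximation: n = 2 × (1.960 + 0.842)² × 0.50² / 0.244² = 65.9, so 66 per arm.
- Exact t-test: 66.9, so 67 per arm, with 80.1% power at 67.
- Dropout: 67 / 0.87 = 77.01, matching 77 enrolled.

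The plan's figure is reproduced. It uses no covariates, so the covariate rule does not affect the planned sample size.

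**2. Chance entry.** Assume a term unrelated to treatment and outcome, with the two tests independent.

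- One term enters: 1 − 0.90 × 0.85 = 0.235.
- At least one of nine enters: 1 − 0.765⁹ = 0.910. With eight: 1 − 0.765⁸ = 0.883.
- Average number entering: 9 × 0.235 = 2.1.
- Imbalance test alone, at least one of nine: 1 − 0.90⁹ = 0.613. With eight: 0.570.
- Possible models per outcome: 2⁹ = 512.

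These figures assume independent terms. With an assumed pairwise correlation of 0.3, the 91% falls to about 86%.

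**3. Entry of real predictors.** Assume r = 0.2 and 134 participants (2 × 67). By Fisher's z, such a covariate enters about 83% of the time. Three independent ones all enter about 0.83³ = 57% of the time.

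**4. Agreement across outcomes.** If association tests for two outcomes were independent, the selected sets would differ with probability 1 − (1 − 0.90 × 2 × 0.15 × 0.85)⁹ = 0.904. The cognitive outcomes are correlated, so the true figure is lower.

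**5. Test size and power, by simulation.** The set-up was 67 per arm, effect 0.244, SD 0.50 and nine independent normal candidates, using ordinary regression without cluster effects. The documents give no covariate R², so a range was assumed.

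All nine terms fixed versus the rule, 10,000 trials per scenario:

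| Assumed R² | Type I error, rule | Power, all nine fixed | Power, rule |
|---|---|---|---|
| 0 | 5.2% | 76.7% | 78.0% |
| 0.1 | 5.0% | 81.3% | 80.7% |
| 0.3 | 4.4% | 90.3% | 88.9% |

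The unadjusted test gave 4.3% in the trials of the last row, so the low value there is not produced by the rule.

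Age, sex and education fixed versus the rule, with three prognostic candidates at r = 0.2 each (ranges are across two runs):

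| Which three are prognostic | Power, fixed | Power, rule | Fixed minus rule |
|---|---|---|---|
| The demographics | 83.7–83.8% | 81.8–82.5% | +1.3 to +1.9 |
| One demographic, two others | 79.5% | 81.2% | −1.7 |
| Three diabetes or imaging variables | 78.4–78.7% | 81.2–82.0% | −2.5 to −3.6 |

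**The case against.** The strongest case against is that the candidates and thresholds are written down, type I error is unharmed, the trial calls itself a pilot, and a fixed set can do worse.

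- **Prespecification.** The candidates and cut-offs are indeed stated. But the model they produce is not, and the screening test is only partly defined.
- **Scope.** The rule follows the exploratory longitudinal model, and the 12-week ANCOVA is described earlier without it. A reader might infer that the rule certainly governs the primary analysis. The text does not say so, but nothing restricts it to the exploratory model either. This is why the point says possibly.
- **Breadth.** A reader might infer that no covariate is fixed, or that the models must differ by outcome and visit. The baseline score is fixed throughout. The sets can differ but might coincide, and the text does not say that selection is repeated at each visit.
- **Test size.** A reader might infer an inflated false-positive rate. Reporting the better of the unadjusted and selected results would give 6.3% to 6.7%, but the plan does not propose that choice.
- **Power.** A reader might infer that the rule costs power. The sign changes with which covariates are prognostic. The documents present cerebrovascular disease as the main route from diabetes to cognitive loss (B3a), so leaving WMH and atrophy out of a fixed set is a contestable choice with a possible cost.
- **Completeness.** Fixing the covariates leaves another data-driven step: "If the three-way interaction term is statistically significant it will be retained in the final model". This stands as a limit on what the change achieves.

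**Conclusion.** The point holds as a prespecification gap. All listed covariates other than the baseline score are chosen by significance tests on trial data, one of which uses the outcome, and the plan does not exclude the primary 12-week ANCOVA from this.

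The 91% chance that at least one irrelevant term enters assumes nine independent, non-prognostic terms. It is 88% with eight variables and lower under correlation. Applied mechanically, the rule keeps type I error near 5%. The power difference is within about 4 points and has no consistent direction. These results rest on assumed covariate strengths and a simplified model without cluster effects.

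The documents therefore do not support a claim of inflated test size, a definite loss of power or a wrong sample size. The change is still worth making, because it removes a data-driven choice from the primary result and needs only wording.

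**What to change.** - Delete both p-value rules.
- Before unblinding, name one covariate set for the 12-week primary ANCOVA and all cognitive outcomes, chosen on prior prognostic grounds, and label that model primary. One example is baseline score, age, sex and education, with WMH and atrophy added if the investigators expect them to be prognostic.
- Put the remaining listed variables in one prespecified sensitivity model.
- Reconcile D2j, where WMH is unconditional in the imaging analysis, with D6, where it is conditional.

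The candidates are already obtainable from the planned history, medication review, medical chart, baseline blood test and MRI (Table 2; D2j; section E), and the sample size does not change. The downside is a few degrees of freedom if a fixed covariate proves uninformative, and up to about 2 to 4 points of power if a prognostic candidate is left out. That second cost is the reason to decide deliberately on WMH and atrophy.
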